Preliminary data also supports the safety of re-irradiation of the upper abdomen in patients with pancreatic/peri-ampullary tumors who have previously been treated with conventionally fractionated radiation regimens. In 2013, Herman et al. published their institutional experience of re-irradiation in a group of 18 patients. (32) No grade 3 or greater toxicities were reported with a dose of 5 Gy x 5; reported one-year local control rates were 62%, and 57% of patients who had symptoms of pain before treatment

experienced pain relief. This data provides initial support for exploring a 5 Gy x 5 regimen in patients with a history of radiation treatment in the upper abdomen.

Considering the difficulty of surgical re-exploration due to extensive adhesions after previous resection, the risks of surgery and general anesthesia for patients who often have impaired performance status, and the prolonged time course and inferior local control associated with conventional CRT, we propose that SBRT may be a viable alternative treatment option for patients who have failed other modes of therapy through local recurrence or local progression. The paucity of studies focusing on this population and lack of a standardized treatment paradigm for these patients underscore the need for further investigation. The recent studies delineated above suggest that Linac-based respiratory gated SBRT is a safe and promising therapeutic option for pancreatic and periampullary cancers that merits further study in the specific patient population that will be treated using this protocol. However, further investigation of pancreatic SBRT should be performed in patients who have been more heavily pre-treated with intensive chemotherapy regimens such as FOLFIRINOX (5-FU, irinotecan, oxaliplatin), and gemcitabine in combination with nab-paclitaxel, which are currently commonly used in this setting but were not part of the standard approach in the previously cited phase I and II studies of pancreatic SBRT.

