# 3.2 Secondary Objectives

- To estimate rates of late (> 3 months after treatment) grade 2 gastritis, enteritis, fistula, and ulcer, or any other grade 3 or greater gastrointestinal toxicity in patients treated with Linac-based SBRT for pancreatic or periampullary cancers
- To estimate rates of local progression, overall survival, metastasis-free survival, and progression-free survival in patients with pancreatic or periampullary cancers treated with fractionated Linac-based SBRT.
- To evaluate the ability of Linac-based SBRT to provide pain control in patients with pain related to a pancreatic or periampullary tumor.
- To evaluate quality of life in patients undergoing treatment with Linac-based SBRT for pancreatic or periampullary cancers.

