#### 3.3.2 Secondary Outcome Measures

• Late (> 3 months after treatment) toxicity rates (as raw percentage), as related to the RTOG Late Radiation Toxicity Grading Scale.

- One-year rates of overall, progression-free, and metastasis-free survival (will
  continue to obtain data on these outcomes at subsequent visits beyond 1
  year, but the 1 year time point will represent the outcome measure of
  interest)
- Pain control at one and three months after treatment (based on reporting of standard pain score (0-10) with an option to record pain score based on FACES assessment scale) –will continue to obtain data on pain control at subsequent visits but these 2 time points will represent the main outcome measures of interest
- Quality of life at each follow-up visit (measured by EORTC QOL-Q scale) will
  continue to obtain data on quality of life at subsequent visits but these 2 time
  points will represent the main outcome measures of interest

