#### 11.4 Analysis Datasets

- Enrolled Population The enrolled population consists of all patients who enroll in the study.
- Efficacy Population The efficacy population comprises all patients who meet
  the eligibility criteria, are registered onto the study, get at least one session of
  Linac-based SBRT, and have at least one follow-up evaluation. This set will be
  used for efficacy analysis.
- Safety Population The safety population comprises all patients who have received at least one session of Linac-based SBRT. This set will be used for safety analysis.

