# 11.10 Analysis of Secondary Objectives

Acute toxicities according to CTCAE 4.0 will be summarized by frequencies and rates calculated as the proportion of patients in the safety population experiencing SAEs, discontinuations due to AEs, and AEs for the two cohorts combined. For the secondary objective of estimating rates of late (> 3 months after treatment) grade 2 gastritis, enteritis, fistula, and ulcer, or any other grade 3 or greater gastrointestinal toxicity, the proportion of patients with each condition and its 90% confidence interval will be calculated.

In Cohort B only, Kaplan-Meier estimates will be used to estimate the median and 90% confidence intervals for time to local progression, overall survival, metastasis-free survival and progression-free survival. The 1-year rates and 90% confidence intervals will be also be estimated from these curves. A listing of clinical outcomes will be generated for Cohort A.

Pain control (based on reporting of standard pain score (0-10) with the option to use the FACES 0-10 scale) will be evaluated before and after Linac-based SBRT and the change in pain scores will be evaluated and summarized through descriptive statistics separately for each cohort. For Cohort B, linear mixed models will be used to model changes in pain over time. A similar approach will be used for the EORTC QOL-Q scale.

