# 11.12 Subgroup Analysis

No subgroup analyses are planned other than the separation of efficacy analyses for Cohorts A and B.

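### The pain objective concerns patients with tumor pain, but the planned pain analysis sets no baseline-pain condition, so patients starting at 0 dilute the answer to that objective

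*Combined protocol and SAP*

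**What the plan says.** The objective in section 3.2 names a population: "To evaluate the ability of Linac-based SBRT to provide pain control in patients with pain related to a pancreatic or periampullary tumor". The matching outcome in section 3.3.2 is "Pain control at one and three months after treatment", measured on a 0-10 score, with no mention of pain at baseline.

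Section 11.10 plans two analyses. For both cohorts, "the change in pain scores will be evaluated and summarized through descriptive statistics separately for each cohort". In addition, "For Cohort B, linear mixed models will be used to model changes in pain over time". It names no baseline threshold, restriction or covariate for either.

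The sections around it do not supply the condition. Pain is not an entry requirement in 4.1 or 4.2. The efficacy population in 11.4 asks for eligibility, registration, one SBRT session and one follow-up evaluation. Section 11.12 says "No subgroup analyses are planned other than the separation of efficacy analyses for Cohorts A and B".

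Section 2.3 cites a re-irradiation series in which relief was reported for "57% of patients who had symptoms of pain before treatment". There the denominator is patients with pain at the start.

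**The concern.** The objective asks what happens to pain in patients who have it. As far as the text goes, the analysis describes the change in score across a whole cohort, whether or not a patient had pain. These are different quantities when some patients enter without pain.

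The scale fixes the direction of the difference. A patient at 0 cannot improve, so each such patient contributes a zero or an increase. Real relief in patients with pain could then be reported as a small average change. The median, which section 11.1 lists among the standard summaries, could show no change at all. Because 11.12 plans no subgroup analysis beyond the cohort split, an analysis by baseline pain added later would not be pre-specified.

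**Working it through.** **No figure to reproduce.** The documents give no effect size, standard deviation, power or precision for pain. What follows is an algebraic result and an illustration.

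**Inputs**
- From the documents: a 0-10 scale (3.3.2, 11.10) and about 30 patients expected in Cohort B and 6 in Cohort A (11.5).
- Assumed: share with baseline pain, p, from 30% to 80%; mean change in patients with baseline pain, d1 = -2.0 points; mean change in patients starting at 0, d0 = 0 or +0.5.

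**Formula.** Mean change over all patients = p × d1 + (1 - p) × d0, with d0 never below 0.

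- If d0 = 0, this is p × d1. The retained fraction is p, whatever value d1 takes.
- If d0 > 0, the retained fraction is p + (1 - p) × d0/d1. With d1 negative, this is less than p.

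**Numbers (d1 = -2.0)**

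| p | All-patient mean, d0 = 0 | All-patient mean, d0 = +0.5 | Baseline-pain set | Patients with pain, of 30 |
|---|---|---|---|---|
| 30% | 0.3 × (-2) = -0.6 | -0.6 + 0.7 × 0.5 = -0.25 | -2.0 | 9 |
| 50% | 0.5 × (-2) = -1.0 | -1.0 + 0.5 × 0.5 = -0.75 | -2.0 | 15 |
| 60% | 0.6 × (-2) = -1.2 | -1.2 + 0.4 × 0.5 = -1.0 | -2.0 | 18 |
| 80% | 0.8 × (-2) = -1.6 | -1.6 + 0.2 × 0.5 = -1.5 | -2.0 | 24 |

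**Median.** If more than half of a cohort starts at 0 and stays at 0, the median change is 0 whatever happens to the patients with pain.

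**Mixed model.** Its average time trend in Cohort B is taken over the same mix of patients. With no restriction or baseline term named, it is diluted in the same way.

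**Precision of the restricted set.** Assume a standard deviation of change of 2.5 points. The approximate 90% half-width is 1.645 × 2.5/√n = 4.11/√n, which gives 1.37 points for n = 9, 1.06 for n = 15, 0.97 for n = 18 and 0.84 for n = 24. In Cohort A, 30% to 80% of 6 is about 2 to 5 patients, which supports only a listing or simple description.

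**The case against.** **The all-patient reading is an inference.** Section 11.10 does not say that everyone is included. It sits under the secondary objectives, and one could argue that it silently inherits the 3.2 population. This stands in part: a reader might infer that the plan expressly averages over all patients, and it does not. But 11.4 defines the set used for efficacy without a pain condition, and 11.12 rules out further subsets. An analyst following those sections would use whole cohorts. If a restriction is intended, it is unwritten.

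**Bias depends on the target.** The all-patient mean is a valid estimate of average change in treated patients, and it fits the unrestricted outcome wording in 3.3.2. New pain in a patient who starts at 0 is also informative, since the background section links local progression to pain. This stands. A reader might call the estimate biased without qualification. That is true only relative to the 3.2 objective.

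**The remedy has its own problems.** Selecting on baseline score without a control arm invites regression to the mean, which favors apparent benefit. A score above 0 also admits pain from other causes and misses tumor pain held at 0 by analgesics, which 7.4.2 permits. Both points stand and must be stated with the result. They do not remove the mismatch.

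**Much is already available.** Section 10.1 defines clinical response by relief of pain or other symptoms thought to come from the index lesion, and 11.1 allows exploratory analyses. However, those response categories mix pain with other symptoms, set no denominator of patients with baseline pain, and are not linked to 11.10.

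**The stakes are low.** This is one secondary objective in a pilot with no pain hypothesis or decision rule. A reader might infer that a planned comparison with the 57% figure in 2.3 fails. No such comparison is planned; the figure shows only that the cited series used the restricted denominator.

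**Conclusion.** The point holds as a mismatch between the stated objective and the analysis as specified. Relative to 3.2, patients with a baseline score of 0 can move the mean change only toward no benefit, and they can set the median to 0 if they are the majority and stay at 0. The direction follows from the scale and needs no assumption.

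The size is not known. The retained fraction of the mean effect equals the share with baseline pain if pain-free patients stay at 0, and is smaller if some develop pain. A reader might want to state a particular loss as a finding. Any such percentage only restates an assumed share, because the documents give neither that share nor an expected change.

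No sample size claim or decision rule depends on pain. This is a cheap improvement, not a flaw that threatens the trial.

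**What to change.** In section 11.10, define the analysis set for the 3.2 pain objective as patients with baseline pain: a score above 0, or another threshold stated in advance, attributed to the tumor where that is recorded. For this set:

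- report its n in each cohort;
- report the change in score at one and three months, and fit the Cohort B mixed model in it;
- report the proportion improved and the proportion pain-free, with improvement defined beforehand.

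Keep the all-patient summary alongside it, and within that summary report new pain among patients who start at 0. Adjust 11.12 so that this set is not read as an unplanned subgroup.

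**Cost.** A few sentences. The calendar in section 9 already schedules pain questionnaires before treatment and at follow-up, so no new score is collected. Section 11.1 lets the analysis plan change without a protocol amendment unless a significant feature changes.

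**Downsides to state with the results.** The set is smaller and its intervals wider. Some of the fall may be regression to the mean, because patients are selected on baseline score and there is no control arm. A score above 0 is only a proxy for tumor-related pain.

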# 11.11 Interim Analysis

No interim analyses are planned other than assessing Grade 4 or 5 treatment-related AEs after every  $6^{\rm th}$  patient.

# 11.12 Subgroup Analysis

No subgroup analyses are planned other than the separation of efficacy analyses for Cohorts A and B.

#### 12. DATA FORMS AND SUBMISSION SCHEDULE

This study will utilize electronic Case Report Form completion in the OnCore® database. A calendar of events and required forms are available in OnCore®. The OnCore® database is a comprehensive, web-based, Clinical Trial Management System (CTMS) which utilizes an Oracle database. OnCore® was developed by Forte Research Systems, Inc. and is used by the IUSCC Clinical Trials Office (CTO) and supported by the Indiana Clinical and Translational Sciences Institute (CTSI).

OnCore® provides users secure access with unique IDs/passwords and restricts access by assigned roles, from any location, to record, manage, and report on data associated with the operation and conduct of clinical trials.

All source documents are to remain in the patient's clinic file. All documents should be kept according to applicable federal guidelines. Clinical trial data in OnCore® are periodically monitored by the IU Simon Cancer Center Data Safety Monitoring Committee.

Participant data that will be collected include the following:

- Eligibility or inclusion/exclusion criteria
- Patient demographics
- Pre-study evaluation

- Surgical procedures, with dates and findings (including EUS, biopsy (if needed), fiducial placement, and/or stent placement (if recommended)
- Scan dates (PET/CT (if available) and/or CT)
- Treatment planning date
- Pre-Study labs including hematology, chemistry, and tumor markers (CBC, CMP, and CA 19-9)
- Radiation therapy dates and toxicities reported
- Follow-up evaluations including H&P data, laboratory studies, imaging, and toxicity data
- QOL and pain questionnaires
- Subject study withdrawal, date, and reason
- Participant report of compliance with protocol prescribed medications, specifically PPIs and antiemetics

#### 13. PATIENT CONSENT AND PEER JUDGMENT

The protocol and informed consent form for this study must be approved in writing by the appropriate Institutional Review Board (IRB) prior to any patient being registered on this study.

Changes to the protocol, as well as a change of principal investigator, must also be approved by the Board. Records of the Institutional Review Board review and approval of all documents pertaining to this study must be kept on file by the investigator (housed in the Radiation Oncology Research Office or Clinical Trials Office) and are subject to inspection at any time during the study. Periodic status reports must be submitted to the Institutional Review Board at least yearly, as well as notification of completion of the study and a final report within 3 months of study completion or termination.

The study will be conducted in compliance with ICH guidelines and with all applicable federal (including 21 CFR parts 56 & 50), state or local laws.

#### 14. DATA AND SAFETY MONITORING PLAN

Investigators will conduct continuous review of data and patient safety. Monthly review meetings for moderate risk trials are required and will include the principal investigator, clinical research specialist and/or research nurse (other members per principal investigator's discretion). Monthly meeting summaries should include review of data, the number of patients, significant toxicities as described in the protocol, and responses observed. Summaries will be submitted and reviewed monthly by the IUSCC Data Safety Monitoring Committee (DSMC). Submit to [contact].

# 14.1 Study Auditing and Monitoring

All trials conducted at the IUSCC are subject to auditing and/or monitoring. Reports will be reviewed by the full DSMC at the time of study review. Moderate risk trials are reviewed annually by the DSMC.

#### 14.2 Early Study Closure

At any time during the conduct of the trial, if it is the opinion of the investigators that the risks (or benefits) to the patient warrant early closure of the study, this recommendation should be made in writing to the DSMC. Alternatively, the DSMC may

Protocol Version Date: 07/02/2024 Page 23

initiate suspension or early closure of the study based on its review of the investigator reports.

# 14.3 Reporting Guidelines

The DSMC has streamlined the reporting process by utilizing reports from OnCore®. This has allowed direct view of reports within the Clinical Trials Management System (CTMS); thus discontinuing paper reports. SAE reports are entered into OnCore® monthly and reviewed by the DSMC chair and/or coordinator monthly. Findings will be reported to the full DSMC at the time of study review.

# 14.4 Reporting Death

Death will be reported per local IRB reporting guidelines.

# 14.5 Study Accrual Oversight

Accrual data will be entered into the IUSCC OnCore® system. The Protocol Progress Committee (PPC) reviews study accrual twice per year while the PPC coordinator reviews accrual quarterly.

#### 14.6 Protocol Deviations

Protocol deviations are entered into OnCore® and reviewed by the DSMC chair and/or coordinator monthly. Findings will be reported to the full DSMC at the time of study review.

# 15. REPORTING ADVERSE EVENTS

Low-grade toxicities are to be expected given the disease profile. Any toxicity below CTCAE v4.0 grade 3 will not be reported on the Master AE Log or Case Report Forms. However, this information will be retained in patient charts. Towards end of life, hospitalization events increase within this patient population. Unplanned hospitalizations that occur greater than 30 days from the last fraction of SBRT and that are not attributable to research intervention will be recorded on the Master AE Log and reported at the time of continuing review and SMC monitoring. These parameters are drafted in accordance with CFR21, and provide realistic expectations based on the sickness of this patient population.

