# 8. TOXICITIES TO BE MONITORED/DOSAGE MODIFICATIONS

It is difficult at this time to predict with confidence the percentage risk of complications from the proposed Linac-based SBRT treatment. However, it is reasonable to extrapolate from the current experience with radiotherapy in and around the pancreas. Based upon prior phase I and phase II studies, we anticipate that the toxicities associated with this treatment will be acceptable. We estimate that ≤20% of patients will experience grade 2 or higher late Radiation-related GI toxicity within one year. Late GI toxicities are those events occurring more than 3 months after Linac-based SBRT. Acute GI toxicities are those events occurring within 3 months following Linac-based SBRT. Acute toxicities commonly associated with such treatment include nausea, vomiting, fatigue, anorexia and weight loss. Severe side effects such as gastrointestinal (GI) obstruction, perforation, or hemorrhage are uncommon complications, occurring in <5% of patients undergoing standard radiation therapy for pancreatic cancer. The major serious toxicity in this group of patients is the development of duodenal/gastric ulcers. Most of these are successfully managed medically. However, Stanford has observed 2 cases of duodenal perforation associated with Linacbased SBRT. We anticipate that because of refinements in radiation treatment planning techniques and because the dose will be divided over five treatments (as opposed to one), the biological equivalent and actual dose to the duodenum will be less than prior studies.

Although we expect a comparable rate of complications with fractionated Linac-based SBRT, it is important to note that vomiting, GI obstruction, GI hemorrhage, anorexia and weight loss are also commonly associated with pancreatic cancer progression. Clinical and radiographic assessments will be performed in an effort to identify these effects, ascertain their etiology and provide the most appropriate palliative measures. Hepatic and renal radiation toxicity is not anticipated given the expectation of limited incidental irradiation of these organs and we have not observed any to date in the patients treated with Linac-based SBRT. Complications, if any, will be graded according to the CTCAE, National Cancer Institute, version 4.0 (see Appendix I). We will also utilize the RTOG scale for grading acute and chronic radiotherapy toxicities.

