# 15.1 Definitions of Adverse Events

# 15.1.1 Adverse Event (AE)

An **adverse event** is defined as untoward medical occurrence associated with the use of a medical intervention in humans, whether or not considered related to the medical intervention. An adverse event can be **ANY** unfavorable and unintended sign (e.g. an abnormal laboratory finding), symptom, or disease temporarily associated with the use of a medicinal (investigational) product, whether or not considered related to the medicinal (investigational) product (attribution of 'unrelated', 'unlikely', 'possible', 'probable', or 'definite'). Acute adverse events will be graded according to the NCI Common Toxicity Criteria, Version 4.0.

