# 15.3 Adverse Event (AE) and Serious Adverse Event (SAE) Reporting

Acute adverse events (CTCAEs) will be recorded from the time of first SBRT and for at least 90 days after treatment discontinuation, regardless of whether or not the event(s) are considered related to SBRT. All Acute AEs considered related to SBRT will be followed until resolution, return to baseline, or deemed clinically insignificant, even if this occurs post-trial.

All SAE's should be collected from the first fraction of SBRT until death or the patient enrolls in hospice. SAE's related or possibly related to study treatment or a study procedure should be reported until the patient is off study. Any death occurring within 30 days after the last fraction of SBRT or last study procedure must be reported as an SAE regardless of attribution.

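### Late grade 2 gastritis, enteritis, fistula and ulcer are a secondary endpoint, but Section 15 keeps all toxicity below grade 3 off the study's data forms

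*Combined protocol and SAP*

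**What the plan says.** The first secondary objective in Section 3.2 is "To estimate rates of late (> 3 months after treatment) grade 2 gastritis, enteritis, fistula, and ulcer", together with any other gastrointestinal toxicity of grade 3 or above. Section 11.10 gives the analysis: "the proportion of patients with each condition and its 90% confidence interval will be calculated". It names no data source.

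Section 15 sets the recording rule: "Any toxicity below CTCAE v4.0 grade 3 will not be reported on the Master AE Log or Case Report Forms". It adds that the lower-grade information stays in patient charts. No carve-out is given for late events or for the four named conditions.

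On grading scales the text is mixed. Section 3.3.2 describes the late outcome as "toxicity rates (as raw percentage), as related to the RTOG Late Radiation Toxicity Grading Scale". Section 15.1.1 says "Acute adverse events will be graded according to the NCI Common Toxicity Criteria, Version 4.0", and Section 11.10 says "Acute toxicities according to CTCAE 4.0 will be summarized by frequencies and rates". Section 8, however, states without limit of time that "Complications, if any, will be graded according to the CTCAE, National Cancer Institute, version 4.0", and then applies the RTOG scale to both acute and chronic effects.

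On recording windows, Section 15.3 says "Acute adverse events (CTCAEs) will be recorded from the time of first SBRT and for at least 90 days after treatment discontinuation", and has SAEs collected until death or hospice enrolment.

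**The concern.** The endpoint needs grade 2 events, and the recording rule stops collection on the study forms one grade higher. A rule followed exactly as written would remove the very events that the objective names. The loss runs in one direction only: events can be omitted but not added, so the reported proportions could only be too low.

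This matters because safety is the declared focus of the study, and Section 8 singles out duodenal and gastric ulceration as the main serious toxicity in these patients. Ulcer is one of the four conditions. Section 8 also states the expected late gastrointestinal toxicity (at most 20% within a year) at grade 2 or higher. A dataset that starts at grade 3 could not be compared with that expectation.

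**Working it through.** This is a conflict between sections, so most of the check sets them side by side.

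1. **What the endpoint needs.** Sections 3.2 and 11.10: grade 2 events in four conditions, more than 3 months after treatment, as a proportion per condition.

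2. **What reaches the forms.** Section 15: only grade 3 and above. Grade 2 is below that floor.

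3. **Whether another section lifts the exclusion.**
   - Section 12 lists toxicities reported with the radiation therapy dates, and toxicity data from follow-up evaluations. No grade or scale is given, and a general list does not clearly override a specific exclusion.
   - The Section 9 calendar schedules an AE evaluation at 4–6 weeks, at 3, 6, 9 and 12 months, and every 6 months in years 2–5. That fixes when patients are assessed. Section 15 governs what is then entered.
   - Sections 15.1.2 and 15.3.2 bring SAEs into OnCore. A grade 2 event enters by that route only if it also meets a seriousness criterion.
   - Section 15.3 states recording windows for acute AEs and for SAEs. None is stated for non-serious late events.
   - No section describes abstraction from charts into the study database.

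4. **Effect on the estimate.** If the objective means grade 2 or higher, grade 3+ cases of the four conditions would still be on the forms and the proportion would be understated. If it means grade 2 exactly, only those that qualify as SAEs would be counted. Either way the error is downward.

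5. **Size.** Section 11.5 sets enrolment at 38. For one condition, the change in the proportion per omitted patient is 1/n. With n = 38, 1/38 = 0.0263, or 2.6 percentage points. A smaller denominator makes the step larger, so 2.6 points is the minimum per patient whose only qualifying event for that condition is left off.

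6. **What cannot be computed.** The number of patients so affected is not in the documents. Section 2.2 cites a single-fraction study in which 7 of 15 patients had grade 2 or higher gastrointestinal toxicity and 2 of 15 had grade 3 or higher, so 7 − 2 = 5 of those 7 were grade 2 only. That split rests on seven patients, comes from a different regimen, and covers all gastrointestinal toxicity rather than the four conditions. I have not used it to estimate the bias.

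**The case against.** The strongest reply is that the Section 15 floor is written in CTCAE grades, and the protocol mostly reserves CTCAE for acute events. Sections 11.10, 15.1.1 and 15.3 all pair the two, while Section 3.3.2 puts the late outcome on the RTOG scale. On that reading the floor never touches the endpoint. This is plausible, and it is why the scope is arguable. It does not settle the matter. Section 15 refers to any toxicity, not to acute toxicity. Section 8 grades complications by CTCAE and uses RTOG for acute and chronic effects alike, so there is no clean division by scale. The same Section 15 paragraph also covers hospitalizations more than 30 days after SBRT with no upper limit. This last point is weaker support, since that rule turns on timing and attribution rather than grade and starts inside the acute period. Even on the RTOG reading, no form, log or recording window is stated for non-serious late events.

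Three further points stand:

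- The OnCore forms are not part of the documents, and a form that captures late grade 2 events may exist.
- The data are recoverable. Charts are retained, outside records must be reviewed at the centre, and this is one site with at most 38 patients.
- The step of 2.6 points is a property of n = 38, not an estimate of bias.

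These limit the consequence but do not remove the conflict in the text.

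**Conclusion.** The concern holds. As written, the Section 15 recording floor conflicts with a stated secondary endpoint, and following it would bias the four late grade 2 rates downward. The size is unknown: at least 2.6 percentage points for a condition per patient whose only qualifying event is left off, with no basis in the documents for counting such patients. The bias arises only if the analysis relies on forms that follow Section 15 and no chart abstraction is done.

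The primary endpoint, the grade 4–5 stopping rule and the grade 3 or higher part of the late-toxicity objective are not affected. This should be fixed before analysis but does not threaten the main result. Confidence is moderate, because the intended scope of the floor is arguable and the forms cannot be seen.

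**What to change.** - Amend Section 15 to exempt late grade 2 gastritis, enteritis, fistula and ulcer from the grade 3 floor. The floor can stay for everything else.
- Record these four conditions on the electronic case report form at the follow-up visits that already include an AE evaluation, through the end of follow-up, and state that recording window in Section 15.3.
- Name one grading scale for this endpoint and reconcile Sections 3.3.2, 8, 11.10, 15, 15.1.1 and 15.3 with it.
- State the data source for late toxicity in Section 11.10.
- For patients already treated, abstract these events from retained charts and outside records before analysis.

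The cost is one form item covering four conditions, completed at existing visits over up to five years, plus chart abstraction for at most 38 patients. Sample size, treatment and the primary analysis do not change.
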